4.14 Safety and Tolerability Evaluation

Refer to the individual modules.

4.14.1 Exposure and treatment administration

Exposure to investigational product i.e. total amount of study drug received will be listed for all patients.

Total treatment duration will be summarized by the following: mean, standard deviation, minimum, maximum, median and number of observations. Exposure is also measured by the number of cycles received. A cycle corresponds to a period of 28 days from cycle 2 and 35 days for cycle 1. If a cycle is prolonged due to toxicity, this should still be counted as one cycle. A cycle will be counted if treatment is started even if the full dose is not delivered. In addition, the number and percentage of

patients with at least one dose reduction will be presented separately for the initial period of evaluability defined as 35 days and for any cycle in the study.

Relative dose intensity (RDI) of AZD0466 will be derived as the percentage of the actual dose delivered relative to the intended dose up to treatment discontinuation as:

$$RDI(\%) = 100 \times d/D$$

where:

d is the actual cumulative dose delivered up to the last dosing, and

D is the intended cumulative dose up to the last day of dosing
(i.e. that would have been delivered without a modification of the dose or schedule).

Summaries by mean, standard deviation, minimum, maximum, median and number of observations will be produced for RDI of AZD0466.

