The DDI part of Module 2 (Cycle 1) will be performed in 3 periods over 21 days (Table 25), as follows:

- Period 1 (Days 1-10): AZD0466 infusion on Days 1, 4, and 8
- Period 2 (Days 11-14): Voriconazole administration bid
- Period 3 (Days 15-21): AZD0466 infusion on Day 15 (at the Day 1 equivalent dose) in combination with voriconazole bid on Days 15-19.

Module 2 Cycle 1 (DDI Part) will utilise a target dose of AZD0466 that has been declared tolerable in the dose escalation Part A of Module 1 (Table 22). After reaching the target dose at Day 8, there will be a dose reduction at Day 15 to the Day 1 equivalent dose, and thereafter there will be a return to the full target dose.

In Module 2 Cycle 2 (after the DDI part), patients may receive AZD0466 as monotherapy at a higher target dose, if a new higher AZD0466 dose level was declared tolerable in Module 1. This dose increase may be implemented without a dose ramp-up. This will allow patients to continue to receive study treatment at a tolerated dose within the predicted efficacious dose range in humans (see Section 11.1.3.1).

Patients who do not wish to continue receiving AZD0466 will undertake the follow-up assessments detailed in Section 7.

Table 22 Module 2 AZD0466 Dose Guidance

AZD0466 Dose*				
Module 2, Cycle 1				Module 2, Cycle 2 and Beyond
D1 RU	D4 RU	D8 TD	D15 (dose equivalent to D1 dose)	D1, D8, D15, D22
75 mg	150 mg	300 mg ^a	75 mg	300 mg weekly ^b
150 mg	300 mg	600 mg ^a	150 mg	600 mg weekly ^b
300 mg	600 mg	1200 mg ^a	300 mg	1200 mg weekly ^b
600 mg	1200 mg	2400 mg ^a	600 mg	2400 mg weekly ^b
1200 mg	2400 mg	3600 mg ^a	1200 mg	3600 mg weekly ^b
2400 mg	3600 mg	5400 mg ^a	2400 mg	5400 mg weekly ^b

^a Module 2 Cycle 1 will utilise a target dose of AZD0466 that has been declared tolerable in the dose escalation Part A of Module 1.

^b Patients may receive AZD0466 after Cycle 1 of Module 2 at a higher target dose, without dose ramp up required, if a subsequent AZD0466 dose level has been declared tolerable in Part A of Module 1.

* Doses displayed are for guidance only. Definitive target and ramp-up doses will be decided by the SRC in Module 1 and communicated accordingly.

D, day; RU, ramp up; SRC, Safety Review Committee; TD, target dose.

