12.12.1 Exposure and treatment administration

For the calculation and presentation of exposure and treatment administration for AZD0466 refer to Section 4.14.1.

In addition, the exposure to voriconazole received will be listed for all patients. Actual and total treatment duration will be summarized by the following: mean, standard deviation, minimum, maximum, median and number of observations.

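### SAP 12.12.1 applies Module 1's 35-day Cycle 1 and dose-reduction window to Module 2, where Cycle 1 is 21 days, and leaves open how the planned Day 15 dose and a permitted target increase enter the exposure summaries

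*SAP*

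**What the plan says.** SAP 4.14.1 sets the exposure rules for the whole study.

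- Cycle length: "A cycle corresponds to a period of 28 days from cycle 2 and 35 days for cycle 1".
- Cycle counting: "A cycle will be counted if treatment is started even if the full dose is not delivered".
- Dose reductions, as a count and a percentage: "patients with at least one dose reduction will be presented separately for the initial period of evaluability defined as 35 days". A second summary covers all cycles.
- RDI is 100 × d/D. Here d is the cumulative dose delivered, and D is the intended cumulative dose up to the last dosing day, explained as the amount "that would have been delivered without a modification of the dose or schedule".

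For Module 2, SAP 12.12.1 says: "For the calculation and presentation of exposure and treatment administration for AZD0466 refer to Section 4.14.1". Its only addition is voriconazole exposure.

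Protocol 12.1.5 says that the drug-drug interaction (DDI) part, Cycle 1, "will be performed in 3 periods over 21 days", and Protocol Table 25 also heads Cycle 1 as 21 days. After the target dose on Day 8, "there will be a dose reduction at Day 15 to the Day 1 equivalent dose". From Cycle 2, "patients may receive AZD0466 as monotherapy at a higher target dose" if Module 1 has declared a higher level tolerable. SAP 11.1 repeats all three statements.

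The SAP does not define a dose reduction. It does not say whether the planned Day 15 dose, or a permitted increase, is a modification or part of the intended dose.

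**The concern.** The 35 days are Module 1's figure: they match its Cycle 1 and its DLT evaluation period (Protocol 11.4.1 and 11.4.7.1; SAP 4.14.2). Module 2 has a shorter Cycle 1, and its analysis sets (SAP Table 8) contain no DLT-evaluable set, so there is no period of evaluability for the window to describe. Carried over, the window pools dosing in the DDI cycle with dosing after it.

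The second problem is ambiguity. Module 2 builds in one dose below target and allows one change above it. SAP 11.1 uses the words dose reduction for the first, and D excludes modifications of dose. Two programmers could follow the text and produce different reduction percentages and RDIs for the same fully compliant patient.

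Module 2 was ongoing when recruitment stopped and is analysed under this SAP, with safety and tolerability as the primary objective. At the planned 10 to 14 patients, one patient moves a percentage by 10 points (1/10) to 7.1 points (1/14).

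**Working it through.** **1. Cycle length.** Module 1 Cycle 1 is a 7-day ramp-up plus 28 days (Protocol 11.4.1): 7 + 28 = 35 days, which reproduces the SAP figure. Module 2 Cycle 1 is Days 1–10, 11–14 and 15–21 (Protocol 12.1.5): 10 + 4 + 7 = 21 days. The core rule is 35 − 21 = 14 days too long for Module 2.

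**2. What the 35-day window holds in Module 2.** Infusions fall on Cycle 1 Days 1, 4, 8 and 15, then on Cycle 2 Days 1, 8, 15 and 22, which are study days 22, 29, 36 and 43. Day 35 is Cycle 2 Day 35 − 21 = 14. The window therefore holds study days 1, 4, 8, 15, 22 and 29. The last two come after voriconazole ends on Day 19 (Protocol 12.4.1) and may already be at a higher target.

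**3. Number of cycles.** Counted by treatment start, as SAP 4.14.1 provides, the count is correct. Only if cycles were derived from elapsed days would it change: a last dose on study day 22 or 29 would give 1 cycle instead of 2, and on day 50 or 57 would give 2 instead of 3.

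**4. RDI after a fully compliant Cycle 1.** Doses in mg are the guidance values in Protocol Table 22, used only for arithmetic. With the planned Day 15 dose in D, RDI is 100% in every row. With Day 15 in D at target:

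| Target | Delivered (Days 1, 4, 8, 15) | D with Day 15 at target | RDI |
|---|---|---|---|
| 300 | 75+150+300+75 = 600 | 825 | 72.7% |
| 600 | 150+300+600+150 = 1200 | 1650 | 72.7% |
| 1200 | 300+600+1200+300 = 2400 | 3300 | 72.7% |
| 2400 | 600+1200+2400+600 = 4800 | 6600 | 72.7% |
| 3600 | 1200+2400+3600+1200 = 8400 | 10800 | 77.8% |
| 5400 | 2400+3600+5400+2400 = 13800 | 16800 | 82.1% |

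**5. RDI after a one-level increase and one full Cycle 2 (four doses), with D kept at the Cycle 1 target.**

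| Increase | d | D, Day 15 as planned | RDI | D, Day 15 at target | RDI |
|---|---|---|---|---|---|
| 300 to 600 | 600+4×600 = 3000 | 600+4×300 = 1800 | 166.7% | 825+1200 = 2025 | 148.1% |
| 2400 to 3600 | 4800+4×3600 = 19200 | 4800+4×2400 = 14400 | 133.3% | 6600+9600 = 16200 | 118.5% |
| 3600 to 5400 | 8400+4×5400 = 30000 | 8400+4×3600 = 22800 | 131.6% | 10800+14400 = 25200 | 119.0% |

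The 600-to-1200 and 1200-to-2400 increases give the same percentages as the first row.

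**6. Effect on what RDI shows.** Take 300 to 600 mg, with two of the four Cycle 2 doses given at 300 mg: d = 600 + 2×600 + 2×300 = 2400. Against D = 1800 (Day 15 as planned, Cycle 1 target kept), RDI is 133.3%. Against a D that follows the assigned target, 600 + 4×600 = 3000, RDI is 80%.

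**7. After the fix.** With Day 15 and any newly assigned target in D, a fully compliant patient has RDI 100% and no reduction, and study days 22 and 29 fall outside the Cycle 1 window.

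**The case against.** The strongest reply is that a sensible reading avoids most of this. D is the intended dose, and the Day 15 dose is intended for every Module 2 patient, with its own column in Table 22. In the protocol, dose modification is the heading for toxicity management (Section 6.6), not for planned dosing. On that reading Day 15 is no reduction and a compliant Cycle 1 has RDI 100%. This stands to the extent that the SAP does not compel the other reading. A reader might infer that every patient dosed on Day 15 will be shown as reduced, or that RDI will exceed 100% after an increase. The text permits those results but does not require them.

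A reader might also infer that reductions made for toxicity would be hidden. The documents do not support that. The eCRF records dose reductions with their reason (Protocol 6.4). SAP 4.14.4, which SAP 12.12.2 applies to Module 2, tabulates AEs leading to dose reduction and lists the action taken.

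Nor do the core rules fit Module 1 alone: total amount received, treatment duration and cycle counts by treatment start work in both modules.

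It can be added that core Protocol 6.6.1 also uses 35 days, for haematological dose modifications, so the figure is not found only in Module 1. That section still places the 35 days within Cycle 1, which Module 2's 21-day cycle cannot contain, and it does not give Module 2 a period of evaluability.

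Finally, these are descriptive summaries in at most 14 planned patients, with no hypothesis test. That limits the consequence but does not repair the window.

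**Conclusion.** The 35-day window is wrong as written for Module 2. It is 14 days longer than Cycle 1 and takes in two Cycle 2 infusions, whatever reading is taken elsewhere.

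The Day 15 and RDI points are gaps in definition, not certain errors. A compliant Cycle 1 can show 100%, or 72.7% to 82.1%. After a one-level increase and one further cycle, RDI is 100% if D follows the new target and includes Day 15 as planned. If D keeps the Cycle 1 target, it is about 132% to 167% with Day 15 as planned, or about 119% to 148% with Day 15 at target. The 72.7% and the 167% rest on different treatments of Day 15 in D and should not be cited as one scenario. All RDI figures assume the Table 22 guidance doses and full compliance; actual doses may differ.

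Cycle counts are sound if taken by treatment start, and toxicity-related reductions remain visible in the AE tables.

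**What to change.** Add a short paragraph to SAP 12.12.1 for Module 2:

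- Cycle 1 is 21 days.
- Dose reductions are reported for Cycle 1 and for any cycle, in place of the 35-day period.
- A reduction is a dose below the one planned for that visit, so the planned Day 15 dose is not a reduction.
- D follows the planned or currently assigned dose, including Day 15 and, from the date of assignment, any higher target. Target increases are tabulated separately.

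This changes analysis definitions only, not dosing. The cost is the paragraph and the matching output specification; the dosing data are already collected.

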4.14.2 Dose limiting toxicities (DLTs)

A DLT is defined as an AE or abnormal laboratory value that meets the predefined study DLT criteria as described in Section 11.4.7.2 in the study protocol. The DLT evaluation period is defined from first dose of study treatment, up to the end of Cycle 1 (Day 35). DLTs occurring during this period will be used for determination of the maximum tolerated dose (MTD) during Part A in Module 1.

The number of patients evaluable for determination of DLTs and the number of patients with any DLT (and their categorisation) during the DLT evaluation period will be summarised by dose level/cohort, and by SOC and PT, as appropriate.

The listings and tables will be based on the DLT-evaluable analysis set.

4.14.3 Definition of Maximum Tolerated Dose and Definition of Recommended Phase II Dose

The MTD evaluation will be based on the DLT-evaluable population. The MTD will be determined by isotonic regression analysis applied to DLT rates observed during the dose-escalation phase. The estimated MTD will be selected as the dose with the smallest absolute value of difference between the estimated DLT rate and the target DLT rate of 30% among all doses. If 2 or more doses tie for the smallest difference, the following rules will be applied:

If the estimated DLT rate is < 30% for all doses, then select the higher dose among the tied doses

If the estimated DLT rate for the tied doses are a combination of < 30% and > 30% then select the higher dose among the tied doses

If the estimated DLT rate is > 30% for all doses, then select the lower dose among the tied doses.

The MTD evaluation will not be part of this analysis and thus related methods are not further be described in this analysis plan. The RP2D and schedule will be determined in discussion among the SRC (Appendix A 5 of the study protocol) and the sponsor. Observations related to PK, PD, and AEs may be included in the rationale supporting the RP2D and schedule.

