2.1 Primary Objective

Objectives	Endpoints/Variables
To assess the safety and tolerability of AZD0466 in patients with advanced haematological malignancies	Incidence of AEs and SAEs Changes from baseline in laboratory findings, physical examinations, performance status, electrocardiograms, and vital signs

For further and more detailed definitions of primary study objectives refer to the individual modules.

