6.1 Primary Objective

Objectives	Endpoints/Variables
To assess the safety and tolerability of AZD0466 in patients with advanced haematological malignancies	DLT MTD RP2D and schedule

DLT, dose-limiting toxicity; MTD, maximum tolerated dose; RP2D, recommended Phase II dose

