8.10 Efficacy Evaluation

The preliminary antitumor activity of AZD0466 will be estimated using the following endpoints:

- Complete response,
- OS.

All of the collected response related data, such as from complete blood count (CBC), extramedullary disease status, bone marrow core biopsy and aspirate will be listed for all patients in the Intention-to-treat analysis set. Summaries will not be produced.

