8.10.2 Primary Efficacy Endpoints

8.10.2.1 Complete Response (CR+CRi) Rate

Complete response rate (CR+CRi) for AML and ALL patients is defined as the proportion of patients with best response as complete remission (CR) or incomplete haematological response (CRi), as determined by criteria described in Section 3.2.1 and in Appendix J and Appendix K in the study protocol. Any treated patient who has not satisfied the criteria for CR or CRi will be treated as a non-responder for this analysis.

Data obtained from first dose up until treatment failure or disease progression, or the last evaluable assessment in the absence of treatment failure or disease progression, will be included in the assessment of CR+CRi, regardless of whether the patient withdrew from study treatment.

The complete response rate will be presented along with all remaining response categories, as defined in Section 3.2.1 by means of the proportion (%).

The analyses will include all patients from the Evaluable for Response analysis set. Patients who went off treatment without a response or who received a subsequent therapy after treatment failure or disease progression, and then respond will not be included as responders in this evaluation.

Secondarily, the analyses will be repeated for the Intention-to-treat analysis set, for that the denominators for the calculation of percentages will refer to the number of patients in the Intention-to-treat analysis set. Patients who are not evaluable for response analysis will not be assigned to a response category and frequencies for missing data items will not be presented.

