8.12 Safety and Tolerability Evaluation

Safety, tolerability and DLT data will be listed and summarised as defined by the current AZ standards (oncology early phase study outputs).

Safety analysis set will be used for all safety and tolerability analyses. All listings and tables, other than those to assess DLTs during Cycle 1 in Part A, will be based on the safety analysis set. To describe the DLTs during Cycle 1 in Part A, the DLT-evaluable analysis set will be used.

Part A includes the AEs, AESIs, laboratory data, vital signs, ECG, LVEF (by MUGA/ MRI/ ECHO) as safety assessments. The listings and tables of all safety data for Part A will be created as described in this section. In addition, for Part A, DLTs will be listed and summarised; MTD (if determined) will be reported.

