8.13 Determination of Sample Size**8.13.1.1 AZD0466 Monotherapy Escalation - Part A**

The primary objective of Part A is to identify the MTD and RP2D of AZD0466 monotherapy. In Part A, 3 to 12 DLT-evaluable patients may be treated in each dose level using an mTPI-2 design ([Guo et al 2017](#)) permitting up to a maximum of 30 DLT-evaluable patients for dose exploration. In addition, any tolerated dose level may be expanded at the discretion of the sponsor in discussion with the SRC to include up to a total of 18 patients for further evaluation of PK, PD, safety, or biological efficacy. Up to a total of 58 patients will be enrolled to yield a maximum of 30 DLT-evaluable patients and 18 patients for further exploration in Part A. This limits the number of patients exposed to AZD0466 consistent with the expected safety profiles of the study treatment, but includes sufficient patients to explore safety of the treatment, PK and effects on pharmacodynamic biomarkers, and to collect preliminary efficacy data.

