13 CHANGES IN THE CONDUCT OF THE STUDY OR PLANNED ANALYSIS

As per the protocol, Section 11.7.6, analysis of efficacy data from Module 1 was to include data from Part B of Module 1. As Module 1 Part B was not initiated, and if data allow, the analyses described in Section 11.7.6 of the protocol will be applied to Module 1 Part A data.

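### The SAP leaves the MTD, a listed Part A primary endpoint, without an analysis or a declared change, and its sections disagree on TTR, DoR and the interval for the CR rate

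*SAP*

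**What the plan says.** **MTD.** SAP 6.1 gives the Part A primary endpoints as "DLT MTD RP2D and schedule". The sample size section, 8.13.1.1, is more pointed: "The primary objective of Part A is to identify the MTD and RP2D of AZD0466 monotherapy". SAP 4.14.2 says that DLTs in the 35-day window serve to determine the MTD. SAP 4.14.3 then specifies isotonic regression on the DLT-evaluable set, selection of the dose whose estimate is closest to 30%, and three tie rules. It ends with "The MTD evaluation will not be part of this analysis and thus related methods are not further be described in this analysis plan". SAP 8.12 nevertheless states "MTD (if determined) will be reported", and 8.12.3 only points back to 4.14.3.

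**Efficacy.** SAP 6.2 keeps TTR and DoR as secondary endpoints, and Table 6 gives each an analysis set. SAP 8.10 opens with "The preliminary antitumor activity of AZD0466 will be estimated using the following endpoints" and lists two, complete response and OS. SAP 8.10.2.1 presents the CR rate "by means of the proportion" and mentions no interval. Section 13, on changes to the planned analysis, says "if data allow, the analyses described in Section 11.7.6 of the protocol will be applied to Module 1 Part A data". Protocol 11.7.6 calls for an exact 95% CI on the CR rate and Kaplan-Meier analysis of TTR and DoR.

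**The concern.** A primary endpoint should have either an analysis or a declared reason for having none. Here the MTD has a method, an exclusion and a conditional promise to report, and the three do not fit together. Someone working from the SAP would produce no MTD output, yet the report is expected to carry an MTD if there is one, from a source the SAP does not name. At stake is the step from raw DLT counts to an estimated dose-toxicity relation with its uncertainty, which the isotonic rule was meant to supply.

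The efficacy sections raise a lesser version of the same difficulty. Depending on which section is followed, TTR, DoR and the interval for the CR rate are either produced or not.

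**Working it through.** The plan states no figure that needs reproducing. The check is mainly textual; all counts below are assumed, because the documents give no DLT or response data.

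**1. Can Section 13 restore the MTD analysis?** Section 13 carries over protocol 11.7.6 only, which is the efficacy section. The MTD method is in protocol 11.4.7.3, so the carry-over does not reach it. Section 13 has no other entry, so the exclusion in 4.14.3 is not declared there.

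**2. What of the primary objective is still planned?**
- SAP 4.14.2: numbers evaluable for DLT and numbers with a DLT, by dose level, on the DLT-evaluable set. These give the observed rate at each dose.
- SAP 2.1 also names "Incidence of AEs and SAEs" as a primary endpoint, and 4.14.4 plans extensive AE summaries.
- SAP 4.14.3: the RP2D is settled by the SRC and the sponsor.

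What is missing is the isotonic estimate and the formal MTD selection.

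**3. What would the rule return if it were run?** Isotonic estimates do not decrease with dose: p1 ≤ … ≤ pK. If all are below 0.30, the distance 0.30 − pk is smallest at the largest estimate, which belongs to dose K, and the tie rule takes the higher dose. The rule therefore always names the highest tested dose in that case, including when no DLT has occurred. The one-sided 95% upper bound for zero events in n is 1 − 0.05^(1/n):
- 0/3: 1 − 0.05^(1/3) = 0.632
- 0/6: 1 − 0.05^(1/6) = 0.393

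Both exceed the 30% target, so such data would not show that the top dose is the MTD.

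**4. Do the SAP and the protocol agree on ties either side of 30%?** Take two tied doses with assumed estimates of 20% (1/5) and 40% (2/5), and no other dose closer. Then |0.20 − 0.30| = |0.40 − 0.30| = 0.10. SAP 4.14.3 takes the higher dose, with the 40% estimate. Protocol 11.4.7.3 takes the highest tied dose at or below 30%, with the 20% estimate. The two documents give different answers on the same data.

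**5. Efficacy sections side by side.**

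| Item | SAP 6.2 and Table 6 | SAP 8.10 and 8.10.2.1 | SAP 13 via protocol 11.7.6 |
|---|---|---|---|
| TTR | kept | not listed | Kaplan-Meier, conditional on data |
| DoR | kept | not listed | Kaplan-Meier, conditional on data |
| CR rate interval | not addressed | none stated | exact 95% CI, conditional on data |

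SAP 4.2 sets confidence levels for intervals where they are presented; it does not say that the CR rate gets one.

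**6. What does leaving out the interval cost?** For an assumed 1/6 (16.7%), the lower exact limit is 1 − 0.975^(1/6) = 0.0042. The upper limit solves (1 − p)^6 + 6p(1 − p)^5 = 0.025, giving p = 0.641. The interval is 0.4% to 64.1%. For an assumed 3/36 (8.3%) it is 1.8% to 22.5%.

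**The case against.** The best defence is the termination. Recruitment stopped on 16 June 2023 with Part A still running, and the sponsor ended the study on 28 July 2023. Protocol 11.7.5 times the Part A final analysis from when the MTD has been determined, so the MTD can be seen as an input to that analysis. On that reading, 4.14.3 and 8.12 are compatible: the MTD is not estimated here, and is reported if the escalation process established one. This is plausible and lowers the severity. It does not close the gap, because the SAP neither gives termination as the reason nor says where the determination is made.

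A reader might go further and infer that Part A's primary question has no planned answer. The documents do not support that: the stated objective is safety and tolerability, and step 2 shows that most of it is covered.

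A reader might also infer that TTR, DoR and the CR interval are excluded just as the MTD is. They are not. No sentence excludes them, and Section 13 brings them back conditionally. They are also secondary endpoints, so they do not bear on the primary question.

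Finally, SAP v2.0 is dated 14 December 2023, after the planned last visit of 8 August 2023, in an open-label study. It is tempting to conclude that analyses were chosen with the results in view. The dates make that possible, but nothing shows it. No hypothesis is tested, and the SAP's amendment history openly records the removal of the TTR and DoR sections.

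**Conclusion.** The point holds in a limited form. The SAP drops evaluation of a listed primary endpoint without declaring it in Section 13 and without saying where the MTD would be determined, while 8.12 still refers to one. What is lost is the formal MTD estimate and its uncertainty; the observed DLT counts by dose are kept. Separately, 8.10 conflicts with 6.2, Table 6 and Section 13 on TTR and DoR, and 8.10.2.1 conflicts with Section 13 on the interval for the CR rate. The different rules for ties either side of 30% must be reconciled before any MTD is reported.

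The textual conclusion rests on no numerical assumption. The sizes quoted (upper bounds of 63% and 39%, and a CI of 0.4% to 64.1%) depend on assumed counts and only show the order of uncertainty at small cohort sizes. This should be fixed, but in a terminated, descriptive study it does not invalidate the remaining analyses.

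One further inference should be resisted: that the lower edge of the 30% ± 5% target, 25%, marks an MTD as not reached. No document uses it that way. Protocol Table 10 uses observed counts only to guide escalation, where 2/8 and 3/12, both exactly 25%, lead to escalation.

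**What to change.** - In SAP 4.14.3, replace the exclusion with a descriptive table on the DLT-evaluable set. For each dose level give the observed DLT rate and the isotonic estimate, with an exact or posterior 95% interval.
- Report the MTD, or state that it was not determined and why (for example, early termination). Do not let the rule automatically label the highest tested dose as the MTD when all doses tie below target.
- Reconcile the tie rules in SAP 4.14.3 and protocol 11.4.7.3 first.
- Say in 8.12 where and by whom the MTD is determined, and declare any dropped MTD analysis in Section 13.
- Add the exact 95% CI for the CR rate to 8.10.2.1.
- Make 6.2, Table 6, 8.10 and Section 13 agree on TTR and DoR, either keeping them with their method or declaring them dropped.

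The cost is one small table covering at most seven dose levels (DL-1 and DL1 to DL6 in protocol Table 4), one added interval, and SAP wording. No new data are required.
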